We will analyze the caregiver questionnaire outcomes and the death outcome using a longitudinal GLMM or GEE model appropriate for the outcome type since the data will be collected at multiple time points after discharge. Count data that tend to have more than 0 or 1 events counted will be analyzed using a Poisson model while binary or count data that rarely goes beyond 1 occurrence will be analyzed using a Logistic model. In case of count data that rarely goes beyond 1 occurrence, this data will be transformed to binary data (occurrence/no occurrence). We will present mean outcome ratios for count data (from Poisson models) and odds ratios for binary data (from logistic models) with respect to the intervention effect as well as 95% CI of the intervention effect. All analyses will be adjusted for repeated measures over time, so that patterns of change for these outcomes over time can be assessed by treatment group.

In addition to time of discharge and 24 months of age, anthropometric outcomes will be measured at birth. We will calculate anthropometric z-scores at each of the three assessment periods for the purpose of analysis based on age and gender specific WHO norms. The approach to analyzing weight is given next.

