We will provide the mean and SD of infants' weights (z-scores) separately for each treatment group. We will use a mixed linear model to evaluate the effect of treatment arm on weight (z-scores). The model will examine how the treatment means differ (i.e., main treatment effect), how treatment means change over time (i.e., main time effect), and how differences between treatment means change over time (i.e., treatment-by-time effect). We will carry out assessment across 3 time points: birth, hospital discharge, and 24 months of age. The mixed model longitudinal analytical approach allows us to analyze correlated data obtained repeatedly from the same participant and account for the ICC among participants nested within with same clinical site. To account for potential imbalance in key demographic and site-level characteristics, unadjusted and adjusted GLMMs will be fit to the data. Initially, the unadjusted mixed model will include the fixed categorical effects of intervention, time, and intervention-by-time interaction and the random-site effect. We will calculate the point estimates and their respective CIs for the changes in infants' weights for each intervention group and for the difference in the estimated change between intervention groups. Additionally, the team will present the p-value of the difference in point estimates between intervention groups.

We will examine the impact of the treatment arm on length, HC, and infant weight for length (z-scores) using the same analytical methods described for weight (z-scores) above. Additionally, we will provide the mean and SD of infant BMI-z at 24-months for each treatment group. The team will use a GLMM with an identity link to compare average BMI-z between the groups, and the team will report point estimates for the group mean difference along with a 95% CI.

To compare Bayley-IV scores between intervention arms, we will perform a linear mixed-effects model with a fixed effect for the intervention group and a random effect for study site. We will report point estimates for the group mean difference along with a 95% CI, and the team will repeat this analytical approach for each of the Bayley-IV domains.

Descriptive statistics (means, medians, SD, percentiles) for continuous secondary outcomes and frequency based statistics (N and percentages) for binary secondary outcomes will be generated and summarized in a tabular form by treatment group.

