4.1 Modeling Process

For the primary outcome (H1), linear mixed model with site as random effect and intervention as a fixed effect will be used.

For safety outcomes, binomial proportions and their corresponding 95% CI by intervention arm for seizure (clinical and EEG), excessive stool output, respiratory disturbances, and feeding intolerance will be reported. Chi-square/Fisher exact tests will be used to compare between the intervention arms. If we end up with a very small number of adverse events and severe adverse events, analysis of these measures will be descriptive only.

For the secondary linear outcomes (H2, H3, H5 & H12d), linear mixed model with site as random effect will be used. For secondary binary outcomes (H4, H6), generalized linear mixed model with site as random effect will be used. For count outcomes (H12a-12c), generalized linear mixed models using either Poisson or negative binomial distribution and site as random effect will be used. Intervention will be included in the models as a fixed effect. Secondary outcome models will be adjusted for breastfeeding status, maternal treatment, and stabilization dose.

Hypotheses H9 – H11 will be analyzed in a similar manner to H2. For the PROMIS model (H10), we will adjust for 1-month after discharge and if mother is the primary care giver as fixed effect covariates.

Hypothesis H8 will be analyzed using latent profile analysis as specified in Liu et al. (2). Model fit indices and likelihood ratio tests will inform the determination for the most-appropriate number of classes.

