6.3 Secondary Outcomes

Secondary outcomes that will be considered during initial analysis will include but not limited to:

• Number of days on morphine from first weaning dose to cessation of opioid for slow- and rapid-wean groups (H2)

- Number of days on methadone from first weaning dose to cessation of opioid for slowand rapid-wean groups (H3)
- Escalation or resumption of opioid during treatment (Y/N scenario)) (H4)
- Total amount of opioid from first weaning dose to cessation of opioid for non-withdrawn infants (H5)
- Initiation and/or escalation of second- or third- line drugs to treat NOWS signs from the first weaning dose to cessation (H6)
- Atypical neurobehavioral profile prior to discharge using the NICU Network Neurobehavioral Scale (NNNS)(H8)
- Length of hospital stay (H9)
- Maternal well-being measured using PROMIS, one month post discharge and at 24-month follow-up visit (H10)
- Maternal-infant attachment measured using MPAQ total scores, one month post discharge (H10)
 - o Maternal well-being
 - o maternal-infant attachment
- Infant growth (H11)
 - o Weight, height, head circumference at 24-month follow-up visit
- Infant wellness after discharge and initial 24 months of age looking at ER and acute care facility visits over time (Y/N for time (1-4)) (H12)
- BISTEA consists of two multi-item scales, a problem scale (31 items) and competence scale (11 items), with high score on the problem scale or a low score on the competence scale being less favorable. (H12). These scores will be converted to percentiles based on BITSEA Examiner's Manual (BITSEA ph2 Manual MapiTrust.pdf)
- Infant development to 24 months of age (H13)
 - o Bayley cognitive, language, and motor performed by a developmental specialist.

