6.4.3 Covariates

All secondary regression models will include the stratification variable (site) as a random effect and will be adjusted for:

- Breastfeeding status
- Stabilization dose, continuous
- Maternal treatment which will be categorized as follow:
 - Methadone use
 - o Buprenorphine ± naloxone
 - Prescribed opioids other than methadone and buprenorphine ± naloxone
 - o None/Unknown

In case of mixing among the 4 groups the following rules will be followed:

- o If methadone is used with other opioid, classify as methadone
- If buprenorphine is used with other opioid, classify as Buprenorphine ± naloxone
- o If methadone is used with buprenorphine, classify based on which drug has been used most proximal to delivery.

Additionally, if the sample size allows, secondary analyses can be adjusted for critical covariates that are substantially imbalanced at baseline (both clinically and statistically significantly different)

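### The SAP's 24-month growth models (H11) do not prespecify the matching birth z-score as a covariate, which loses precision, and they differ from the protocol's growth analysis

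*SAP*

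**What the plan says.** **SAP.** Section 2.2.1 sets Objective 11 as a comparison of growth over the first 24 months, with hypotheses on weight, height and head circumference z-scores that name no time point. Section 6.3 gives the outcome as "Weight, height, head circumference at 24-month follow-up visit". On the model, section 4.1 says "Hypotheses H9 – H11 will be analyzed in a similar manner to H2", that is, a linear mixed model with site random and intervention fixed. The covariates are fixed there too: "Secondary outcome models will be adjusted for breastfeeding status, maternal treatment, and stabilization dose". Sections 6.4.1 and 6.4.3 repeat that list. Section 6.4.3 adds that, sample size permitting, "secondary analyses can be adjusted for critical covariates that are substantially imbalanced at baseline", and it requires the imbalance to be both clinical and statistical. The formula in 6.4.1 also ends with an open term for further covariates and names none. For PROMIS, section 4.1 does use an earlier score: "we will adjust for 1-month after discharge and if mother is the primary care giver as fixed effect covariates".

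**Protocol.** The schedule of activities (Table 3) includes infant measurements at birth in the baseline data. Section 5.1.5 says that, besides discharge and 24 months, "anthropometric outcomes will be measured at birth", and that z-scores will be calculated at all three times. The growth model is longitudinal: "We will carry out assessment across 3 time points: birth, hospital discharge, and 24 months of age". It has treatment, time and treatment-by-time effects. The estimates to be reported are the change in each arm and the between-arm difference in change, with confidence intervals and a p-value.

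**The concern.** Birth size is a pre-randomisation measurement of the same quantity as the outcome. If it predicts size at 24 months, leaving it out puts explainable variation into the residual and widens the interval for the arm effect.

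The route left open in SAP 6.4.3 does not address this. It admits a covariate for being imbalanced, whereas the precision gained depends on the covariate's correlation with the outcome. The SAP is also uneven: the 24-month PROMIS model carries a 1-month score measured after randomisation, while the growth models carry no earlier value.

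Precision is scarce here. SAP 3.4 reports a target lowered to 302 and a trial ended for slow enrolment, and 24-month follow-up will lose more infants. In addition, the two documents describe different growth analyses. If neither is named as governing, the choice could be made after the data are seen.

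**Working it through.** **The plan's own figure.** Neither document gives a power, SD, effect size or correlation for growth. The nearest stated figure is the re-estimated target for the primary outcome (SAP 3.4): difference 2.0 days, SD 6.2, two-sided 0.05, 80% power.

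Total N = 4 × SD² × (1.960 + 0.842)² / difference² = 4 × 38.44 × 7.849 / 4 = 301.7, so 302. This reproduces the SAP.

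**Inputs for H11**
- Two equal arms, two-sided 0.05 (SAP 3.4, 6.4.1).
- Infants at 24 months: 0.60 × 302 = 181. The 60% is the protocol's follow-up figure for the Bayley (5.2.3); applying it to growth is an assumption. Final enrolment may be below 302.
- SD of a z-score: 1 (assumed), equal at birth and 24 months.
- r, the correlation of birth and 24-month z-scores: not in the documents. Range shown: 0.2 to 0.6.

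**Variance of the between-arm estimate**, complete data, relative to the 24-month value alone:
- 24-month value only: 1
- adjusted for birth z-score: 1 − r²
- difference in change, birth to 24 months: 1 + 1 − 2r = 2(1 − r)
- change relative to adjusted: 2(1 − r) / (1 − r²) = 2 / (1 + r)

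The detectable difference at 80% power with 181 infants is 2.802 × √(4/181) = 0.416 z unadjusted. Adjustment multiplies it by √(1 − r²).

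| r | Variance cut by adjustment | Equivalent sample, 1/(1 − r²) | Power if unadjusted is 80% | Detectable z (unadjusted 0.416) | Change: variance vs 24-month only | Change: variance vs adjusted |
|---|---|---|---|---|---|---|
| 0.2 | 4% | 1.04 | 81.6% | 0.408 | 1.6 | 1.67 |
| 0.3 | 9% | 1.10 | 83.6% | 0.397 | 1.4 | 1.54 |
| 0.4 | 16% | 1.19 | 86.4% | 0.382 | 1.2 | 1.43 |
| 0.5 | 25% | 1.33 | 89.9% | 0.361 | 1.0 | 1.33 |
| 0.6 | 36% | 1.56 | 93.8% | 0.333 | 0.8 | 1.25 |

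These gains are upper limits, because site, maternal treatment, stabilization dose and breastfeeding may already explain part of the same variation.

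**Bias check.** In 10,000 simulated trials of 182 infants with a true effect of 0.416, the mean estimates (24-month only, adjusted, change) were 0.416, 0.416 and 0.417 at r = 0.3, and 0.416 for all three at r = 0.5. The variances relative to the adjusted analysis were 1.09 and 1.52 (24-month only, change) at r = 0.3, and 1.30 and 1.33 at r = 0.5, close to the formulas.

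**Protocol model.** The expected arm effect at birth is zero. The difference in change from birth to 24 months therefore estimates the full 24-month effect. Its cost is variance: below r = 0.5 it is less precise than ignoring birth altogether. The protocol does not say over which interval the change is taken; this result is for birth to 24 months. An average over all three times would behave differently: (0 + 0 + 1)/3 = one third of an effect present only at 24 months, and (0 + 1 + 1)/3 = two thirds of an effect equal at discharge and 24 months.

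**The case against.** The strongest reply is that little is at stake. Omitting a prognostic covariate in a randomised comparison does not bias the estimate. H11 is secondary, and SAP 6.4.4 treats everything but the primary analysis as exploratory. The size of the gain rests on a correlation that nobody has stated, and at r = 0.3 power moves only from 80% to 83.6%. SAP 6.4.2 foresees convergence trouble at small centres and allows for fewer covariates, which argues for a short list. The 6.3 list is also described as not exhaustive, so the 24-month reading rests on one bullet. Finally, Protocol 5.1.3 collects weight at the start of the intervention, which is nearer to randomisation than birth weight.

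Most of this stands as a limit on the importance of the point, but it does not remove it. One covariate per model is a small addition, and a birth value exists for all three measures, whereas for the start of the intervention the protocol names only weight. The uncertainty about which time points the SAP analyses is itself a reason to state them.

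A reader might go further and infer that the protocol treats birth as a post-treatment time, so that its growth effect is pulled towards zero. The documents do not support that. Section 5.1.5 includes a treatment-by-time term and reports the difference in change, so birth serves as the baseline. The one-third and two-thirds figures apply only if a main effect averaged over the three times is read as the treatment effect. The SAP's 24-month analysis has no birth time point to dilute it.

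**Conclusion.** The point holds as a matter of precision and of consistency between the documents. The SAP does not prespecify the matching birth z-score for H11, and its imbalance clause would admit it for the wrong reason. For an assumed r of 0.3 to 0.5, adjustment would save up to about 9 to 25% of residual variance, equivalent to 10 to 33% more infants; the gain is minor at 0.3 and worth having at 0.5. The protocol's difference in change from birth to 24 months is unbiased but needs 1.54 to 1.33 times the sample of a birth-adjusted analysis over the same range.

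Two further inferences should not be drawn. The H11 result would not be invalid or biased. Nor do the documents show that birth size is recorded for every infant: it is listed as baseline data, its completeness is not stated, and out-born infants are enrolled. Since H11 is exploratory, this is an improvement to make and no threat to the trial's main conclusion.

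**What to change.** Amend the SAP before the follow-up analysis, which section 3.7 places in July 2026, in one of two ways:

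1. In each H11 model, add the birth z-score of the same measure (weight, length, head circumference) as a fixed covariate, whatever the observed balance, and name the arm difference at 24 months as the estimate.
2. Use the protocol's longitudinal model with arm means constrained equal at birth, and name the 24-month arm contrast as the estimate, so that neither an averaged main effect nor an unspecified change is reported in its place.

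In either case, state whether the SAP or the protocol growth analysis governs, and say how a missing birth value is handled; the covariate imputation in SAP 6.6.2 could be cited for option 1. The cost is SAP wording and one extra covariate per model. No new data collection is needed, since birth measurements are already part of the baseline data.

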6.4 Frequentist Statistical Methods

6.4.1 Statistical Methods

The proposed analyses will be conducted using the intent to treat (ITT) population.

Consort Diagram

Patient accounting will be presented in a consort diagram. This diagram will include:

- Number of infants screened
- Number of infants eligible
- Number of infants consented
- Number of infants randomized
- Number of infants randomized by group
- Number of infants in each medication category
- Number of infants with primary outcome per group per medication

Descriptive Tables

Baseline characteristics and outcomes will be descriptively summarized in the following manner:

Binary (yes/no, 1/0 type) measures will be summarized by level with frequency out of the total non-missing values and percentage of total non-missing values. Percentages will be reported to one decimal place, nn(XX.X%) or nn/NN(XX.X%)

Multiple level discrete measures will be tabulated with one row per level and with a row indicating how many observations had missing data. Percentages will be calculated as percent of all observations associated with a given treatment.

Continuous measures will be summarized by number of non-missing values, means and standard deviation [n: XX.X (XX.X)], or by median with minimum and maximum, or by median with first and third quartile [n: XX.X (XX.X , XX.X)]. Mean, standard deviations, median, minimum, maximum, and quartiles will be reported to one decimal place.

Count data will be summarized using median (min, max).

Statistical Modeling and Inferences

Statistical modeling will be performed using linear mixed model for continuous measures and generalized linear mixed model for binary and count outcomes with logit and log link functions, respectively. All models will include site as random effect and intervention arm as a fixed effect. Secondary outcome models will also be adjusted for maternal treatment, stabilization dose, and breast feeding.

For the ith infant, all models (except the primary) will have the following form $g(\mu_i)$ with g(.) being a monotonic link function and the following form:

```
g(\mu_i) = \beta_o + \beta_1 I(\text{intervention=fast}) + \beta_2 I(\text{Maternal Treatment=methadone}) + \beta_3 I(\text{Materna Treatment= Buprenorphine } \pm \text{ naloxone}) + \beta_4 I(\text{Maternal Treatment=other opioids}) + \beta_5 (\text{stabilization dose}) + \beta_6 (\text{Maternal feed=Yes}) + \beta_i X_i
```

where:

 μ_i = expected value of outcome y_i

 β_0 = intercept, the expected mean number of treatment days when all covariates = 0

 β_1 = Intervention effect of fast vs slow wean interventions

 $\beta_2, \beta_3, \beta_4$ = effect of maternal treatment, compare to no treatment

 β_5 = effect of stabilization dose

 β_5 = effect of breastfeeding

 β_i = effect of the jth covariate added to the model

For normal outcomes, g(.) is the identity link function.

For binary outcomes, g(.) is the logit link function and we will assume that y_i follows Bernoulli distribution. Alternatively, we can follow Zou et al. (2003) and use the natural log function, and we will assume that y_i follows Poisson or negative binomial distribution. Decision will be based on manuscript writing team, if they prefer to report risks vs odd ratios.

For count outcomes, g(.) is the natural log function, and we will assume that y_i either follows Poisson or negative binomial distribution.

All hypothesis tests will be performed using a two-sided significance level of 0.05. Unless otherwise specified, results for each type regression performed will include the following:

- Normal regression
 - Unadjusted
 - Mean (and 95% confidence intervals (CI)) of the outcome in each treatment group.
 - Mean difference (and 95% CI) of the outcome between treatment groups.
 - Adjusted using pre-specified covariates.
 - Mean (and 95% CI) of the outcome in each treatment group.
 - Mean difference (and 95% CI and p-value) of the outcome between treatment groups.
- Logit Binomial regression
 - Unadjusted
 - Rate (and 95% CI) of the outcome in each treatment group
 - Odds Ratios (and 95% CI) of the outcome between treatment groups
 - Adjusted using pre-specified covariates.
 - Rate (and 95% CI) of the outcome in each treatment group
 - Odds Ratios (and 95% CI and p-value) of the outcome between treatment groups.
- Log-Binomial or Poisson regression
 - Unadjusted
 - Risk (and 95% CI) of the outcome in each treatment group
 - Relative risk (and 95% CI and p-value) of the outcome between treatment groups
 - Adjusted using pre-specified covariates.
 - Risk (and 95% CI) of the outcome in each treatment group
 - Relative risk (and 95% CI and p-value) of the outcome between treatment groups.
- Poisson or negative binomial regression
 - Unadjusted
 - Rate (and 95% CI) of the outcome in each treatment group
 - Relative rate (and 95% CI and p-value) of the outcome between treatment groups
 - Adjusted using pre-specified covariates.
 - Rate (and 95% CI) of the outcome in each treatment group
 - Relative rate (and 95% CI and p-value) of the outcome between treatment groups

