The rapidity at which a clinical team can perform weaning with infant tolerance without recurrence of NOWS signs is unknown. In a randomized trial of morphine versus methadone in which clinical teams weaned the drug by 10% of the stabilization dose (18), 48% of morphine-treated and 38% of methadone-treated infants needed dose escalation. With progressive increases in the percent reduction of drug dose, there will, presumably, be an increase in frequency of recurrence of NOWS signs that will mitigate the benefits of more rapid weaning. A 15% reduction of drug dose is large enough to yield important decreases in the length of treatment, which may enable earlier transition out of the hospital and decreasing healthcare costs.

Shortening the weaning phase of NOWS treatment has the potential to impact healthcare costs and minimize the separation of the mother-infant dyad. Opioid use disorder is estimated to occur in 6.5/1000 hospitalizations for infant delivery (30). This allows an estimate of cost savings for infant's ≥ 36 weeks gestations:

- Births per year in the US: $\approx 4,000,000$ births
- Percent births ≥ 36 weeks: $\approx 90\% \times 4$ million $\rightarrow 3,600,000$
- Opioid exposed: 6.5/1,000 deliveries
- Total opioid exposed: $6.5 \times 3600 \rightarrow 23,400$
- Opioid exposed receiving pharmacological treatment: $38.6\% \times 23,400 \rightarrow 9032$
- Cost of care/day: $\$869 \times 9032 \rightarrow \$7,848,808$

A treatment reduction of 2.0 days would reduce healthcare costs by more than \$15.7 million per year across the United States. Potential cost savings would be even greater for hospitals that care for infants with NOWS in facilities with higher levels of care (e.g., NICU, special care nurseries).

If successful, this clinical trial would achieve the overarching goals of research initiatives for NOWS (8). Specifically, it would limit ongoing opioid exposure for infants, minimize separation of the mother-infant dyad, and reduce healthcare expenditures.

SECTION 4. METHODS

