5.1.5. Analyses of Secondary Outcomes

We will use the same approach described in the primary outcome analysis to compare the number of days of opioid treatment with only infants receiving morphine as the primary pharmacological treatment for NOWS (Secondary Outcome 1). We will use this same approach to compare the number of days of opioid treatment using only infants receiving methadone as the primary pharmacological treatment for NOWS (Secondary Outcome 2).

We will use adjusted logistic regression models to provide an odds ratio (OR) and 95% Confidence Intervals (CI) for binary secondary outcomes measured only once. These outcomes will include:

- the proportion of infants by intervention arms that escalate or resume opioid medication during weaning,
- for the proportion of infants by intervention arms with an atypical neurobehavioral profile (**Profile 5, Figure 1**),
- the proportion of infants who receive an escalation of a second-line or third-line drug to treat NOWS signs from the first weaning dose to cessation of opioid.

Title: Pragmatic, Randomized, Blinded Trial to Shorten Pharmacologic Treatment of Newborns with Neonatal Opioid Withdrawal Syndrome (NOWS)

Sponsor: National Institutes of Health

We will adjust these models for the stratification variable (hospital), covariates of maternal treatment and stabilization dose, and baseline variables that may differ between groups by chance. We define the covariates that we may adjust for earlier in this section in the paragraph on other collected data.

We will analyze the secondary outcome of the total opioid exposure from the first weaning dose to cessation of opioid in a similar manner as the primary outcome. We will use a regression model that will include: a fixed treatment effect (intervention arms) and adjustment for the stratifying variable, covariates of maternal treatment and stabilization dose, and baseline variables that may differ between groups by chance as fixed effects. We will include hospital (site) as a random effect. The primary test of interest will be the F-test of the intervention arm effect, and we will report the treatment difference along with 95% CI.

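### For yes/no outcomes (H4, H6) the SAP allows a Poisson or negative binomial alternative with no stated robust variance and leaves odds ratio versus relative risk open, although the protocol fixed the odds ratio

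*SAP*

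**What the plan says.** Protocol 5.1.5 sets the method for once-measured binary secondary outcomes, including opioid escalation or resumption (H4 in the SAP) and escalation of second- or third-line drugs (part of H6): "We will use adjusted logistic regression models to provide an odds ratio (OR"), with 95% confidence intervals. Protocol 5.1.6 also places the Bayesian priors for binary outcomes on the log odds ratio scale.

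SAP 4.1 keeps a mixed model: "For secondary binary outcomes (H4, H6), generalized linear mixed model with site as random effect will be used". SAP 6.4.1 then gives the distribution. The default is clear: "For binary outcomes, g(.) is the logit link function and we will assume that y_i follows Bernoulli distribution". The alternative, introduced by reference to a 2003 methods paper, is a log link under the assumption that the outcome "follows Poisson or negative binomial distribution. Decision will be based on manuscript writing team, if they prefer to report risks vs odd ratios". The SAP gives no date for that decision and does not say whether the team will have seen results.

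The reporting list in SAP 6.4.1 has a further relative-risk entry, "Log-Binomial or Poisson regression". Neither document mentions a robust or sandwich variance, and the 2003 paper is not in the SAP reference list.

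**The concern.** Two things are left open that an analysis plan should close.

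The first is the variance. A Poisson likelihood overstates the variance of a yes/no variable, and a negative binomial likelihood assumes at least as much variance as Poisson. Poisson regression can be used for a relative risk, but only with a variance estimator that corrects this, and the SAP names none. A negative binomial likelihood is not a suitable model for a 0/1 outcome.

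The second is the effect measure. The protocol named the odds ratio. The SAP reopens the choice and gives preference of reporting style as the only criterion.

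H4 is where this matters most. Escalation is a common event, and Protocol 4.3.1 names recurrence of signs and the need to escalate or resume opioid as the potential risks of rapid weaning. Intervals that are too wide err towards missing that risk.

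**Working it through.** **Inputs**
- 151 per arm. This is half the SAP 3.4 target of 302, which reproduces: 2 × (1.96 + 0.8416)² × 6.2² / 2.0² = 150.9, so 151 per arm. Enrolment was then ended early and the final number is not given, so 151 is an assumption.
- H4 rates. Protocol 3.3.4 reports from an earlier trial of 10% weaning that "48% of morphine-treated and 38% of methadone-treated infants needed dose escalation".
- H6 rate. The documents give none for the weaning period. As a proxy I take any secondary medication in Protocol Appendix 2: 223/698 = 31.9%, about 32% (assumption).
- Rare-event contrast. Protocol 5.5.2 expects 3% seizures under slow weaning.
- The 15-point differences between arms are assumptions. The documents state no effect size for H4 or H6.

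**Standard error of the log relative risk, n per arm**
- Correct (binomial): √[(1−p₀)/(n p₀) + (1−p₁)/(n p₁)]
- Poisson, model-based: √[1/(n p₀) + 1/(n p₁)]
- With equal rates p, the ratio is 1/√(1−p), and the true type I error of a nominal 5% test is 2 × [1 − Φ(1.96/√(1−p))].

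| Common rate | SE ratio | True type I error | True coverage of 95% CI |
|---|---|---|---|
| 48% | 1.39 | 0.7% | 99.3% |
| 38% | 1.27 | 1.3% | 98.7% |
| 32% | 1.21 | 1.8% | 98.2% |
| 10% | 1.05 | 3.9% | 96.1% |
| 3% | 1.015 | 4.7% | 95.3% |

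**Power for a 15-point rise.** The estimate varies with the correct SE, while the test uses the reported SE. Power is therefore Φ[(log RR − 1.96 × SE reported)/SE correct].

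For 48% versus 63%: log RR = ln(0.63/0.48) = 0.272; correct SE = 0.105; Poisson SE = 0.156.
- Correct variance: Φ[(0.272 − 0.206)/0.105] = 73%
- Model-based Poisson: Φ[(0.272 − 0.306)/0.105] = 37%

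The same steps give 73% and 48% for 38% versus 53%, and 75% and 55% for 32% versus 47%.

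**One data set, two conclusions.** If 48% and 63% were observed, the relative risk is 1.31. Its interval is 1.07 to 1.61 with correct variance and 0.97 to 1.78 with model-based Poisson variance. The odds ratio is (0.63 × 0.52)/(0.48 × 0.37) = 1.84, with unadjusted p about 0.009. Model-based Poisson gives p about 0.08.

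**Simulation** (1,000 trials per scenario, 151 per arm, no covariates or site effect). At 48% in both arms, model-based Poisson rejects 0.6% of the time, Poisson with a sandwich variance 3.8%, and logistic 4.0%. At 48% versus 63% the three have power 37%, 73% and 74%. A negative binomial with dispersion fixed at 1 has power 16%. When dispersion was estimated, in one test fit, it went to about zero, so the model reduced to Poisson.

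**The case against.** The strongest reply is that the SAP does not prescribe a naive Poisson analysis. Logistic regression is the default. Log-binomial, which has the right variance, is also listed for relative risks. The Poisson option is adopted by citing a published method, whose content cannot be checked from the documents. This stands: a robust variance is unstated, not excluded, and every loss of power above is conditional on model-based variance. It does not remove the gap, because the text describes a likelihood within a random-site mixed model and offers negative binomial on equal terms.

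A reader might infer that the measure will be picked after the results are known. The documents do not support that: they give no timing, and the stated criterion is reporting preference, not significance. They also set nothing that would prevent it.

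A reader might also infer that two available p-values inflate false positives. They do not. In simulations of 302 infants in 12 or 20 hospitals, with 48% in both arms, taking the smaller of the naive Poisson and logistic p-values rejected 4.4% to 4.7% of the time, the same as logistic alone. With an individual-level robust variance, the Poisson and logistic p-values differed by at most about 0.003.

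On importance, the protocol lists escalation as a secondary efficacy outcome. The designated safety outcomes are compared by chi-square or Fisher tests (SAP 4.1), and SAP 6.4.4 calls all non-primary analyses exploratory. Counts and percentages will be shown as well, so a large rise would be visible. These points limit the weight of the concern. Even so, SAP 2.2.1 lists H4 and H6 as main secondary objectives with formal hypotheses, and SAP 6.4.1 tests them at two-sided 0.05.

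**Conclusion.** The concern holds in a conditional form. The SAP permits, as an alternative to a valid default, a model whose distribution does not fit a yes/no outcome. It states no variance correction and reopens an effect measure that the protocol had fixed.

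If the alternative is fitted with model-based variance, log-scale intervals are 27% to 39% too wide at the escalation rates the protocol cites, about 21% too wide at the proxy rate for H6, and essentially unaffected at 3%. The error is conservative: the risk is a missed increase in escalation, with power roughly halved in the 48% versus 63% example, and a conclusion that depends on which measure is reported. To say that intervals will be far too wide for all binary outcomes would go beyond the text.

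The size rests on 151 per arm, on earlier-trial rates under 10% weaning, on assumed 15-point differences, and on the H6 proxy.

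**What to change.** In SAP 6.4.1:
- Name the protocol's adjusted odds ratio from the logistic mixed model as the measure for H4 and H6.
- Delete negative binomial as an option for binary outcomes.
- Delete the sentence that leaves the choice to the manuscript team.
- If a relative risk is also wanted, obtain it by standardisation from the logistic model, or from a Poisson model with a stated robust variance. Add the missing reference if that method is kept.

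A robust variance clustered on hospital needs a small-sample correction. Protocol 5.3 mentions twenty interested hospitals, and SAP 6.4.2 notes few infants in some centers. In simulations with unequal sites and an assumed site SD of 0.4 on the logit scale, the uncorrected clustered sandwich had type I error of about 7% to 9% with 20 hospitals and 10% to 11% with 12.

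SAP 3.7 planned the first-phase analysis for April 2024. If it has been done, report the protocol's odds ratio and disclose any other measure as additional. The cost is SAP wording and routine software options, with no new data.
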